#### 1.0 INTRODUCTION

#### 1.1 Study Rationale

The long-term efficacy and side effects of over-the-counter phytotherapies for men with lower urinary tract symptoms attributable to BPH are unknown, despite wide use of these agents by older men for maintaining "prostatic health." The overall goal of this study is to compare the efficacy of a widely available phytotherapy, extract of Serenoa Repens, against placebo in terms of impact on lower urinary tract symptoms. The phytotherapy selected for study has demonstrated short-term efficacy at relieving lower urinary tract symptoms with minimal side effects in a number of clinical trials. However, a recent NIDDK/NCCAM supported trial of Serenoa Repens at the 320 mg daily dose versus placebo did not demonstrate efficacy in terms of symptom reduction over 12 months of follow-up. As a result, this study is being conducted to compare higher-than-standard (double and triple) doses of this agent to determine its short-term effect on lower urinary tract symptoms and other parameters of BPH disease severity, and whether there is sufficient short-term efficacy and tolerability to merit testing for long-term efficacy in a long-term trial focused on the prevention of BPH progression. Because the study arm will use doses of this agent higher than generally used, participants will be monitored closely for toxicity/tolerability and have their doses slowly increased at 24-week intervals.

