#### 2.0 OBJECTIVES

#### 2.1 Primary objective

The primary objective of CAMUS is to determine if Serenoa Repens reduces the AUA symptom score compared to placebo over 72 weeks of treatment and is well tolerated.

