#### 8.0 STATISTICAL CONSIDERATIONS

#### 8.1 Sample size estimation

The primary goal of this study is to determine the efficacy and safety profile of treatment with *Serenoa Repens* compared to placebo. The primary end point of the study is change in AUA symptom score from baseline to 72 weeks. The sample size estimate is based on the following assumptions: a difference in the change in the AUA symptom score from baseline to 72 weeks of 2 points between the placebo arm and the phytotherapy arm, a common standard deviation of the AUA symptom score of 6 points, a two-group t- test, a one-sided significance level of 0.05 and a statistical power of 90%. A one-sided statistical test will be used since an improvement in the AUA symptom score with therapy (i.e., efficacy of therapy) is of primary interest. To detect the hypothesized difference in the change in the AUA symptom score, a sample size of 157 participants per arm will be required. Therefore, a total of 314 participants will be required for the study. To allow for a 10% dropout rate over the course of the study, 350 participants will be recruited to the study.

To determine the power for evaluating safety by measuring hematology and serum chemistry levels, it is assumed that the underlying probability of a severe or life-threatening adverse event detected by laboratory results for placebo is < 2.5%. With 157 participants in each treatment arm, the power to detect a severe or life-threatening adverse event that occurs with frequency  $\ge 10\%$  in the phytotherapy arm at the one-sided 0.05 significance level is 80%.

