#### 8.2.2 Analyses of the Primary Study Endpoint

The primary endpoint of this study is efficacy as determined by the change in AUA symptom score at 72 weeks. A two-group t-test will be used to compare the phytotherapy arm against placebo. A one-sided significance level of 0.05 will be used.

Mixed models repeated measures analysis will be performed to compare the phytotherapy arm with placebo over time (baseline, 24 weeks, 48 weeks and 72 weeks). This technique will control for intra-patient variation. The final covariance structure to be used in these models will be selected after all of the data have been collected. A significance level of 0.05 will be assumed for these longitudinal comparisons. Regarding multiple comparisons, differences between the two treatment groups with respect to the change in the primary endpoint from baseline to 24 weeks, baseline to 48 weeks, and baseline to 72 weeks will be examined to determine if they are significantly different from zero. If these differences are significantly different from zero, comparisons between specific timepoints (48 weeks versus 24 weeks, 72 weeks versus 48 weeks, and 72 weeks versus 24 weeks) for the primary endpoint will be performed. The Hochberg step-up method will be used for each set of these multiple comparisons. (Hochberg, 1990)

An additional analysis that will be performed using the primary endpoint is a comparison between the phytotherapy and placebo arms with respect to the proportion of participants who achieve at least a 3 point difference (improvement) in the AUA symptom score. These proportions will be compared using Fisher's exact test. A one-sided significance level of 0.05 will be used for this comparison.

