Complete blood counts and serum chemistry measurements will be categorized by severity grade from the NCI Common Toxicity Criteria. For each participant and each time period on a dose level (1-24 weeks = level 1, 25-48 weeks = level 2, 49-72 weeks = level 3), the most severe grade of a laboratory level will be taken. For each dose level and laboratory measure, the proportions of participants who have abnormalities of severity grade 3 or greater will be compared between the phytotherapy and placebo arms using Fisher's exact test. A two-sided 0.05 significance level will be used for these comparisons.

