#### 8.2.4 Safety Analysis

Adverse event data will be summarized by treatment arm to capture the proportion of participants reporting at least one episode of a specific adverse event (incidence table), incidence of adverse events causing withdrawal, and incidence of serious adverse events. The total number of episodes for each event reported (frequency table), and the severity and attribution to treatment arm of each episode reported within body system (severity and attribution table), will also be displayed by treatment arm. Listings of adverse events by participants and event will also be provided. Comparisons of incidence of each adverse event between treatment and placebo will be performed using the two-group chi-square test, or Fisher's exact test when the assumptions for the chi-square test are not tenable. A two-sided statistical test with a significance level of 0.05 will be used for these analyses. In addition, 95% confidence intervals will be computed for differences in proportions of adverse events between study arms.

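### 'Well tolerated' is part of the primary objective, but severe laboratory abnormalities are compared only by tests of no difference, and no interval in the plan is tied to a tolerability conclusion

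*Combined protocol and SAP*

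**What the plan says.** Section 2.1 sets out to learn whether the product "reduces the AUA symptom score compared to placebo over 72 weeks of treatment and is well tolerated". Section 1.1 gives that a use: the trial is to show "whether there is sufficient short-term efficacy and tolerability to merit testing for long-term efficacy in a long-term trial". The primary endpoint covers only the first half: "The primary endpoint of this study is efficacy as determined by the change in AUA symptom score at 72 weeks" (section 8.2.2). No section says what result would count as well tolerated.

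The formal safety comparisons are these:

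- **Laboratory values (8.2.3).** For every laboratory variable within a dose period, the plan states that "the proportions of participants who have abnormalities of severity grade 3 or greater will be compared between the phytotherapy and placebo arms using Fisher's exact" (two-sided, at 0.05). No interval is mentioned.
- **Adverse events (8.2.4).** Each event is compared by chi-square or Fisher: "A two-sided statistical test with a significance level of 0.05 will be used for these analyses". 95% confidence intervals for the differences in proportions are also planned, with no threshold and no stated use.
- **Sample size (8.1).** Safety is framed as detection. The plan assumes that "the underlying probability of a severe or life-threatening adverse event detected by laboratory results for placebo is < 2.5"%, and with 157 per arm "the power to detect a severe or life-threatening adverse event that occurs with frequency" of at least 10% on active treatment is given as 80%, one-sided at 0.05.

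**The concern.** A claim that a regimen is well tolerated is a claim that any excess of harm is small. A test of no difference does not address this. When it rejects, it shows harm. When it does not, it may mean little harm or too few events to tell. For laboratory abnormalities the test result is the only comparative output that section 8.2.3 specifies, so a reader has nothing there from which to judge how large an excess remains possible.

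Tolerability is half of the primary objective and one of the two grounds given for moving to a long-term trial of an agent used above its customary dose. If its meaning is not fixed before unblinding, it will be settled once the results are known, and sparse data would make a reassuring reading easier to reach.

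**Working it through.** **Inputs.** From section 8.1: 157 per arm, placebo below 2.5% (2.5% used as the ceiling), active 10%. From section 8.2.3: two-sided Fisher at 0.05. My assumptions: an active rate of 5% or 7.5%, and a placebo rate of 1% or 2%.

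**The plan's own figure.** For a one-sided 0.05 test of 10% v 2.5%, the normal approximation with continuity correction solves n′/4 × [1 + √(1 + 4/(n′ × 0.075))]² = 157, which gives an effective n′ of 131.5. Power is then

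Φ[(0.075√131.5 − 1.645√(2 × 0.0625 × 0.9375)) / √(0.025 × 0.975 + 0.10 × 0.90)] = Φ[(0.860 − 0.563)/0.338] = Φ(0.88) = 81.0%.

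This reproduces the stated 80%. Exact enumeration of a one-sided Fisher test gives 83.5%.

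**The test that will be run.** Let X and Y be independent binomial counts, active and placebo, with n = 157 each. The miss probability is 1 − Σ P(X = x) P(Y = y) over all pairs with x > y and two-sided Fisher p ≤ 0.05.

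| Placebo | Active 10% | Active 7.5% | Active 5% |
|---|---|---|---|
| 2.5% | 26% | 57% | 87% |
| 2% | 17% | 46% | 81% |
| 1% | 5% | 21% | 58% |

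With no dropout (175 per arm) and placebo at 2.5%, the misses are 20% at 10% and 85% at 5%.

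**What one non-significant result can hide.** Take 12/157 (7.64%) on active and 4/157 (2.55%) on placebo. Fisher p = 0.069. The Wilson 95% limits are 4.43% to 12.88% and 1.00% to 6.37%. The Newcombe limits for the difference of 5.10 points are:

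- upper: 5.10 + √[(12.88 − 7.64)² + (2.55 − 1.00)²] = 5.10 + 5.46 = 10.6 points;
- lower: 5.10 − √[(7.64 − 4.43)² + (6.37 − 2.55)²] = 5.10 − 4.99 = 0.1 points.

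The Fisher result reads as no significant difference, while the interval allows an excess above the 10 − 2.5 = 7.5 points that section 8.1 sets out to detect. The lower limit just clears zero because Fisher is the more conservative method, so here the interval is the more informative output in both directions.

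**Would 7.5 points serve as a pass/fail margin?** Consider a rule that supports tolerability when the one-sided 95% Newcombe upper bound is below 7.5 points. At 157 per arm it passes 98% of the time if both arms are 2.5%, 89% if both are 5%, and 5% if the rates are 10% v 2.5%. But it also passes 67% of the time at 5% v 2.5% and 89% at 3% v 1%. It would pass an observed 6 v 0, where the bound is 7.2 points and two-sided Fisher is significant for harm (p = 0.03). The figure cannot simply be borrowed as a margin.

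**The case against.** A reader might infer that the plan will call the product well tolerated whenever p exceeds 0.05. The documents do not support that: no section states such a rule. Section 8.1 speaks of a safety profile, which fits descriptive reporting, and tolerability will also be judged from tables of incidence, seriousness, withdrawal, severity and attribution (8.2.4), from committee review of every grade 3 to 5 event (6.2, 10.4.3) and by the DSMB (8.5). This stands. The point is that the criterion is missing, not that a wrong one was adopted.

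Nor is it right that the plan has no intervals. Section 8.2.4 has them, and section 6.1 counts an abnormal laboratory finding as an adverse event, so a severe laboratory value recorded as one would also receive an interval. That narrows the gap without closing it: the graded laboratory analysis in 8.2.3 has none of its own, and no conclusion draws on those in 8.2.4.

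The miss rates depend on their conditions. The plan puts placebo below 2.5%, so the 2.5% row is the least favourable one, and the 5% active rate is mine. The 26% also overlaps with a separate matter, that 8.1 computes power one-sided while the analysis is two-sided. Aligning the two would not settle this point: a one-sided Fisher test with placebo at 2.5% still misses 10% in 16.5% of trials (1 − 0.835) and 5% in 79% (1 − 0.207).

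Finally, it is tempting to treat 7.5 points as the plan's tolerability margin. It is the excess that 8.1 sets out to detect, for laboratory events only, and nowhere an excess the sponsor accepts.

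**Conclusion.** The concern holds in a limited form. A positive tolerability conclusion sits in the primary objective with no criterion, the severe laboratory comparison offers only a test of no difference, and the adverse-event intervals feed no conclusion. The test's silence is weak evidence: it misses the plan's own 10% rate in 5% to 26% of trials, and an assumed 5% rate in 58% to 87%, as placebo runs from 1% to 2.5% with 157 per arm. These percentages apply to the Fisher test on a single laboratory outcome and should not be carried over to the chi-square tests. The reasoning does not depend on them: at any power, p > 0.05 does not bound the excess.

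This is a worthwhile correction to the analysis plan. It does not invalidate the design or the primary efficacy analysis.

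**What to change.** - **Section 8.2.3.** For each dose period and laboratory measure, report the difference in the proportion with grade 3 or greater values (active minus placebo) with a 95% score-type interval, such as Newcombe, alongside the Fisher p-value. This matches what 8.2.4 already does for adverse events.
- **Sections 8.2.3 and 8.2.4.** Add the same difference and interval for three pooled outcomes: any grade 3 or greater laboratory value, any serious adverse event, and any adverse event causing withdrawal.
- **Section 8.2.4.** State that any conclusion on tolerability will be worded by the excess that the upper limits exclude, and that a non-significant difference will not be taken as evidence of tolerability.
- **Optional margin.** If the sponsor wants a formal pass/fail rule, it should choose and justify the margin before unblinding, and state that meeting it does not override a significant excess of harm.

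The cost is some SAP wording and a few lines of code, with no new patients, visits or data. The downside is a little more output and a more guarded tolerability statement when event rates are high, because the intervals are then wider.

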#### 2.2 Secondary Objectives

Secondary objectives of the study are to:

- 1. Determine if Serenoa Repens has a beneficial effect on subjective global assessment.
- 2. Assess the impact of Serenoa Repens on the following measures over time:
  - a. BPH Impact Index
  - b. Quality of Life item score from the IPSS
  - c. Nocturia item score from the IPSS
  - d. Peak uroflow
  - e. Post-void residual volume
  - f. Prostate Specific Antigen (PSA) level
  - g. Erectile and ejaculatory function
  - h. ICS*male* Incontinence scale
  - i. Jenkins Sleep Dysfunction scale
  - j. NIH Chronic Prostatitis Symptom Index
- 3. Assess the impact of the assigned treatments on complete blood counts and basic blood chemistries

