#### 4.3 Evaluations during Treatment and Follow-Up

- 4.3.1 Focused physical examination (including height and weight) and digital rectal examination at the 72 week visit.
- 4.3.2 Medical follow-up to include new diagnoses, treatments, hospitalizations, life events at the 4, 12, 24, 28, 36, 48, 52, 60 and 72 week visits.
- 4.3.3 Hematology: CBC and PT at the 12, 24, 36, 48, 60 and 72 week visits.
- 4.3.4 Serum chemistries: serum creatinine sodium, potassium, chloride, bicarbonate, glucose, ALT (SGPT), AST (SGOT) and GGT at the 12, 24, 36, 48, 60 and 72 week visits.
- 4.3.5 Urinalysis, including dipstick at the 72-week visit. If dipstick is positive (greater than 0) for blood or leukocyte esterase, then a specimen will be sent for microscopic analysis.
- 4.3.6 PSA at the 24, 48, and 72 week visits. The PSA measurements will be determined by a central laboratory. Please refer to the Manual of Operations for specimen collection and shipping instructions.
- 4.3.7 Vital signs at the 4, 12, 24, 28, 36, 48, 52, 60 and 72 week visits. (Visits 4, 28 and 52 can be optional phone interviews. A blood pressure monitor will be provided to participants to record blood pressure at home. The participant must agree to give 2 sitting readings to the study personnel.)
- 4.3.8 Uroflow measurement to include: voiding time, flow time, time to maximum flow, peak flow rate, mean flow rate, voided volume and post void residual at the 12, 24, 36, 48, 60 and 72 week visits.

- 4.3.9 Bladder Function, IPSS (AUA Symptom Score plus IPSS Quality of Life questions), and BPH Impact Index questionnaires, at the 12, 24, 36, 48, 60 and 72 week visits.
- 4.3.10 Erectile Function, Ejaculatory Function, NIH-CPSI, Jenkins Sleep Dysfunction Scale and Subjective Global Assessment, and participants' perception about whether they are on active therapy or placebo at the 24, 48, and 72 week visits.
- 4.3.11 Treatment compliance by pill count and provision of assigned study medication at the 12, 24, 36, 48, 60, and 72 week visits.
- 4.3.12 Adverse event assessment at the 4, 12, 24, 28, 36, 48, 52, 60, and 72 week visits.
- 4.3.13 Assessment of all medications, including over-the-counter medications, at the 4, 12, 24, 28, 36, 48, 52, 60 and 72 week visits, or when and adverse event occurs. (Visits 4, 28, and 52 can be omitted if optional phone interview chosen.)
- 4.3.14 Serum for banking at SV1.0 and 72 week visit.

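### The only planned analysis of measured blood counts and chemistries is a grade 3-or-worse proportion that ignores the screening value and has little power for small to moderate shifts

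*Combined protocol and SAP*

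**What the plan says.** Section 2.2, objective 3, is to "Assess the impact of the assigned treatments on complete blood counts and basic blood chemistries". Section 8.2.3 gives the analysis. "Complete blood counts and serum chemistry measurements will be categorized by severity grade from the NCI Common Toxicity Criteria"; for each man and each 24-week dose period "the most severe grade of a laboratory level will be taken"; and for each dose level and laboratory measure "the proportions of participants who have abnormalities of severity grade 3 or greater will be compared" between arms by Fisher's exact test. On the error rate: "A two-sided 0.05 significance level will be used for these comparisons".

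The text mentions no screening value, change from baseline, shift table or continuous analysis for these measures. The same section gives the other secondary measures, including PSA, a mixed model over baseline and weeks 24, 48 and 72.

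The data are richer than the analysis. Blood counts, chemistries and prothrombin time are taken at screening visit 1 (section 4.1.1.4) and at six follow-up visits. For haematology, section 4.3 reads: "Hematology: CBC and PT at the 12, 24, 36, 48, 60 and 72 week visits". Prothrombin time is named neither in objective 3 nor in the laboratory paragraph of 8.2.3.

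The power statement in section 8.1 concerns severe or life-threatening events. It assumes that the probability of such an event "detected by laboratory results for placebo is < 2.5" percent, and says that the power to detect a frequency of 10% or more "in the phytotherapy arm at the one-sided 0.05 significance level is 80" percent.

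**The concern.** The trial tests two and three times the usual dose, tolerability is part of the primary objective (section 2.1), and section 1.1 says the results will inform whether a long-term trial is merited. A drift in a liver enzyme or a blood count across the dose steps bears on that decision even if few men reach grade 3. A grade 3 cut-off discards nearly all the information about such a drift. Leaving out the screening value also forgoes precision and mixes pre-existing abnormalities with new ones. A non-significant grade 3 table could then be read as showing no laboratory effect when the comparison had little chance of finding one.

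**Working it through.** **Inputs.** 157 per arm, placebo rate below 2.5%, active rate 10% or more, one-sided 0.05 (section 8.1); two-sided 0.05 and Fisher's exact test (section 8.2.3). Assumptions of mine: values roughly normal after any transformation, a placebo rate of 1% to 2.5% for a single measure, and shifts of 0.2, 0.35 and 0.5 SD.

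**The plan's own figure.** For 2.5% against 10%, the two-proportion formula with continuity correction at one-sided 0.05 and 80% power is:

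- p̄ = 0.0625; n′ = [1.645√(2 × 0.0625 × 0.9375) + 0.842√(0.025 × 0.975 + 0.10 × 0.90)]² / 0.075² ≈ 128.
- n = (n′/4)[1 + √(1 + 4/(0.075n′))]² ≈ 154 per arm.

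At 157 per arm the same formula gives 81.0%, so the stated 80% reproduces. The test in 8.2.3, however, is two-sided. Exact enumeration of Fisher's test at 157 per arm gives 83.5% one-sided and 74.3% two-sided.

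**Events needed.** With no placebo events, 6 active-arm events are needed for two-sided significance (6 v 0, p = 0.030; 5 v 0, p = 0.061).

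**From a shift to a grade 3 rate.** If the placebo rate is p0, a shift of d SD gives an active rate p1 = 1 − Φ(z − d), where z is the upper p0 point of the normal distribution. For d = 0.35:

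- p0 = 1%: 2.326 − 0.35 = 1.976, so p1 = 2.4%.
- p0 = 2.5%: 1.960 − 0.35 = 1.610, so p1 = 5.4%.

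**Comparison of means.** The noncentrality is d√(157/2) = 8.86d, that is 1.77, 3.10 and 4.43. Power is given for one two-sided t-test at 0.05, and at 0.05/3, which is the strictest Hochberg step for three time points.

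| Shift (SD) | Active rate if placebo 1% / 2.5% | Fisher power, placebo 1% / 2.5% | Means, 0.05 | Means, 0.05/3 |
|---|---|---|---|---|
| 0.2 | 1.7% / 3.9% | 1% / 5% | 42% | 26% |
| 0.35 | 2.4% / 5.4% | 5% / 16% | 87% | 76% |
| 0.5 | 3.4% / 7.2% | 16% / 39% | 99% | 98% |

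**Sensitivity.** Section 8.1 puts the placebo rate below 2.5%, so the 2.5% column is the favourable end for Fisher's test. At a placebo rate of 0.5%, Fisher power is 0.1% for 0.2 SD and 4% for 0.5 SD. Baseline adjustment would help the comparison of means: with an assumed correlation of 0.7 between screening and follow-up values, power at 0.05 rises from 42% to 70% for 0.2 SD.

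**The case against.** The strongest reply is that the plan aims at a different question. Section 8.1 directs the laboratory comparison at severe or life-threatening toxicity, and for that target the two-sided test still has 74% power. Sensitivity to small mean shifts, perhaps within the normal range, is an added aim. This stands as far as it goes: the grade 3 comparison is legitimate and should stay. But objective 3 is worded more broadly than severe toxicity.

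Other parts of the reply limit what may be inferred.

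- A reader might infer that nothing below grade 3 is ever compared between arms. That is too strong. Section 6.1 counts an abnormal laboratory finding as an adverse event, section 6.2 records clinically significant events of any severity, and section 8.2.4 compares the incidence of each event. Section 5.2 also asks investigators to consider a drug effect when a new, persistent blood abnormality appears. This route depends on individual judgement and does not analyse the measured values.
- A reader might infer that a man with a grade 3 screening value counts automatically in all three dose periods. He does not. Screening lies outside every period, so he counts only where the abnormality persists or recurs. Randomisation makes such cases noise rather than bias. Section 3.2 also limits creatinine, ALT, AST, GGT and prothrombin time at entry, though not blood counts, electrolytes or glucose.
- A reader might infer that omitting prothrombin time weakens objective 3. It does not, because that objective names only blood counts and chemistries. The omission is a separate gap.
- The rates in section 8.1 are not stated per analyte, and my calculation treats a worst-of-period grade as one measurement. The power figures are therefore illustrative.

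**Conclusion.** The point holds as a cheap improvement rather than an error in the plan. The only analysis of the measured blood counts and chemistries is a grade 3-or-worse proportion without the screening value. Under the stated assumptions its power is at most about 5% for a 0.2 SD shift and 16% for 0.35 SD, where one unadjusted comparison of means has 42% and 87% (26% and 76% at 0.05/3).

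To say that the comparison has almost no power for any moderate shift would go beyond this: at the 2.5% ceiling a 0.5 SD shift has 39%. The sizes rest on approximate normality, the assumed placebo rates and the chosen shifts, because the documents give neither laboratory SDs nor a shift that would matter clinically. The direction does not depend on the exact values.

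Two smaller points stand beside it. Prothrombin time is collected throughout but has no named laboratory analysis. And the 80% in section 8.1 is one-sided, so it does not describe the two-sided test in 8.2.3.

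**What to change.** In section 8.2.3:

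1. Keep the grade 3-or-worse table. Add a version that counts only on-treatment grades worse than the man's grade at screening visit 1.
2. Extend the mixed-model approach to each blood count component, each chemistry value and prothrombin time. Use the log scale where values are skewed, the screening visit 1 value as covariate, and the visits from week 12 to week 72. This is not identical to the model already planned, which uses baseline and weeks 24, 48 and 72.
3. Report the arm difference with a 95% confidence interval at weeks 24, 48 and 72, the end of each dose period, labelled as descriptive safety estimates.
4. State the laboratory power in section 8.1 for the two-sided test.

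The cost is SAP wording and some programming, with no new visits or samples. The downside is more safety comparisons. Nine chemistries plus prothrombin time at three time points make 30 intervals before any blood count component, so about 30 × 0.05 = 1.5 would exclude zero by chance if there were no effect. The descriptive label should make that plain.
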